Antagonist of the glucagon-like peptide 2 (GLP-2) receptor

*Department of Biomedical Sciences,
University of Copenhagen*

*H-24000668
Date: 06/01/25*

Title: Antagonist of the glucagon-like peptide 2 (GLP-2) receptor

Approved ethical committee ID: H-24000668

Project Group:

[name] [name], PhD (PI)

[name] [name], PhD-student

[name], B.A. Science

[name], Med.-student

[name], cand.scient.

[name] [name]

[name], cand. scient., PhD

[name], cand.scient. PhD

[name] [name], MD, DMSc

[name] Bo [name], DMSc

[name] [name], MD, PhD

Background:

Previous studies have shown that GLP-2 increase abdominal blood flow to the intestines. The studies that reveal this effect are built on results of exogenous distributed GLP-2 and have not investigated the endogenous effects of GLP-2. We have previously performed a single study in healthy males with the use of flow sensitive magnetic resonance imaging (MRI) where supraphysiological doses of GLP-2 injections greatly increased the blood flow in the superior mesenteric artery and portal vein but there were surprisingly no changes after intake of oral glucose. In this study we investigate if physiological doses of GLP-2 will increase the blood flow to the intestines and if different doses of the GLP-2 receptor antagonist (GLP-2(3-33)) can alter these flow changes in humans of both genders.

Aim: We aim to determine the right dose of the GLP-2-receptor antagonist to use in physiological research in healthy humans. We hope to be able to achieve the maximal blocking of the GLP-2 receptor possible and at the same time reduce expenses and infusion volume for the participants in future studies. We thereby hope to characterize the use of the GLP-2 receptor antagonist GLP-2(3-33) as an essential tool in research of the role of the human GLP-2 receptor in bone metabolism and nutrient uptake in the future.

Hypothesis: The hypothesis of this study is that the GLP-2(3-33) can block the effects of GLP-2 on the blood flow to the superior mesenteric artery and the portal vein.

Design:

Randomized, placebo controlled, crossover, single blind design in 10 healthy participants.

Baseline information:

A description of the baseline measured will be presented in a table, including the following measures: Age, Weight, Height, BMI, Hemoglobin, Leucocytes, Vitamin D, Fasting glucose, HbA1c, Sex, and Blood pressure. The data will be presented in Median and range.

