Statistical analysis and graphs:

The flow data is analyzed in Rs studio by a linear mixed model, that pairs the data, and compared the interventions after steady state of the infusion of GLP-2(3-33) antagonist. The primary statistical analysis will be done between the interventions: Physiological dose of GLP-2 injection and highest dose of GLP-2-antagonist infusion + GLP-2 injection and placebo infusion. Furthermore, the data will be presented in GraphPad Prism 10. A data table will present the flow measurements of each intervention, including mean and 95% confidence intervals

Criteria:

[figure not shown]
Inclusion

- 1) Age 18-70 years
- 2) BMI 19-28 kg/m²

Exclusion

- 3) Chronic illness that affects the cardiovascular system or gastrointestinal tract
- 4) Treatment with medicine or supplements that cannot be paused for 12 hours
- 5) Intake of above 14 alcoholic drinks per week or substance abuse
- 6) Liver enzymes (ALAT) above 2 times normal values
- 7) Decreased kidney function (eGFR below 90 or creatinine levels over reference value)
- 8) Low blood percentage (hemoglobin below reference value)
- 9) Any condition or disease that the persons responsible for the study find would interfere with the participation of the study.

Methods and outcomes: Phase-contrast magnetic resonance imaging (PC-MRI) is used to calculate blood flow in the blood vessels: superior mesenteric artery, portal vein, celiac trunk and hepatic artery during the infusion of either saline or GLP-2(3-33) receptor antagonist and injection of GLP-2. The main outcome of the study is blood flow in superior mesenteric artery. On each study day, 8 MRI scans are performed (-32 min to 60 min after start of infusion) and four blood samples are taken. Blood glucose is measured bedside on whole blood. The blood samples collected are kept for analysis of GLP-2(1-33), GLP(3-33) and markers of bone metabolism.

Adverse event:

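### The primary contrast can show that the antagonist reduces the GLP-2 flow response, but nothing planned estimates how much of that response is blocked

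*Combined protocol and SAP*

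**What the plan says.** The Hypothesis section states that "the GLP-2(3-33) can block the effects of GLP-2 on the blood flow to the superior mesenteric artery and the portal vein". The Aim section says "We aim to determine the right dose of the GLP-2-receptor antagonist to use in physiological research in healthy humans" and adds "We hope to be able to achieve the maximal blocking of the GLP-2 receptor possible", to be weighed against expense and infusion volume in future studies. The Design section gives "Randomized, placebo controlled, crossover, single blind design in 10 healthy participants".

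Under Methods and outcomes, "The main outcome of the study is blood flow in superior mesenteric artery". Eight MRI scans are taken on each study day, from -32 to 60 minutes relative to the start of infusion.

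Under Statistical analysis and graphs, a linear mixed model pairs the data and compares interventions once the antagonist infusion is at steady state. The primary comparison is between "Physiological dose of GLP-2 injection and highest dose of GLP-2-antagonist infusion + GLP-2 injection and placebo infusion". The plain reading is highest antagonist dose plus GLP-2 versus placebo infusion plus GLP-2, although the wording is not fully clear. The output is described as "A data table will present the flow measurements of each intervention, including mean and 95% confidence intervals".

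The documents define no percent inhibition, no residual GLP-2 effect, no no-GLP-2 or pre-injection reference for full block, and no rule for what counts as blocking.

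**The concern.** Choosing a dose by how well it blocks needs a measure of blockade: the fraction of the GLP-2-induced rise that a dose removes, and the rise left over. The primary contrast yields a difference in flow. The same difference can come from complete block of a small GLP-2 effect or slight block of a large one, and a p-value below 0.05 reads the same in both cases.

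The Aim is to establish the antagonist as a tool for later work on bone metabolism and nutrient uptake. If a dose is taken forward as blocking while a sizeable GLP-2 effect remains, a null finding in that later work could be misread as GLP-2 having no role. Mean flows by intervention do not settle the matter, because they include resting flow and so do not place the doses on a blockade scale.

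**Working it through.** **The plan's own figure.** The sample size of 10 comes without effect size, SD, alpha or power, so it cannot be reproduced.

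**Inputs.** From the documents: n = 10, crossover, paired comparison, 95% intervals. Assumed: two-sided alpha 0.05 and a paired t test (9 df) standing in for the mixed-model contrast. Let B be flow without GLP-2, E the true GLP-2 rise, f the fraction blocked, and SD the standard deviation of the within-person difference between two interventions. The documents give no E or SD. The Background describes a large flow increase, but at supraphysiological doses and without a number. E is therefore varied from 1 to 5 SDs.

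**Step 1: what the contrast estimates.** Flow under placebo infusion + GLP-2 is B + E. Flow under antagonist + GLP-2 is B + (1 - f)E. The difference is fE. A value of 50 mL/min fits E = 50 with f = 100%, and equally E = 200 with f = 25%. Recovering f needs E, and E needs a reference for B.

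**Step 2: smallest significant difference.** t(0.975, 9)/√10 = 2.262/3.162 = 0.715 SD. Dividing by E in SD units gives the observed blockade at which p falls below 0.05. The power columns use the noncentral t distribution.

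| E (SDs) | Observed blockade needed | P(p<0.05), true 25% block | P(p<0.05), true 50% block |
|---|---|---|---|
| 1 | 72% | 11% | 29% |
| 2 | 36% | 29% | 80% |
| 3 | 24% | 56% | 99% |
| 4 | 18% | 80% | over 99% |
| 5 | 14% | 94% | over 99% |

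**Step 3: the same in mL/min (all values assumed), true blockade 40%.**

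| Rise | SD | Critical difference | As blockade | P(p<0.05) |
|---|---|---|---|---|
| 200 | 40 | 28.6 | 14% | 1.00 |
| 200 | 60 | 42.9 | 21% | 0.96 |
| 200 | 100 | 71.5 | 36% | 0.62 |
| 100 | 60 | 42.9 | 43% | 0.47 |
| 60 | 60 | 42.9 | 72% | 0.21 |

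**Step 4: what a percent-blockade interval would add.** These are simulated median Fieller 95% intervals for 1 minus the ratio of mean rises, n = 10. Rises are independent with equal variance, and the SD is that of the difference in rises, so subtracting a reference scan is taken to add no net noise.

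| Rise | SD | True 40% block | True 90% block |
|---|---|---|---|
| 200 | 60 | about 21% to 56% | about 75% to 105% |
| 200 | 100 | about 6% to 66% | about 64% to 115% |
| 100 | 60 | about -3% to 70% | about 59% to 120% |

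At a rise of 60 and SD 100, about a third of intervals are unbounded. The interval separates a weak from a strong blocker when the rise is large relative to the SD. Otherwise the intervals meet or overlap.

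**The case against.** The strongest reply has four parts.

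- *The documents promise less than complete block.* Maximal blocking is worded as a hope, the hypothesis says only that the antagonist can block, and the Background asks whether doses alter the flow changes. The primary contrast answers that last question. This stands, and the contrast should stay. A reader might infer that a significant difference will be reported as complete or maximal block; the documents set no such rule, so that would be a guess about a future report. The Aim still calls for choosing a dose by how well it blocks, and the plan gives no scale for that.
- *Effect size is visible.* The mixed model estimates a difference, and the table gives means with intervals. This partly stands: a reader could judge size informally. But an interval for each intervention is not an interval for the paired difference or for the fraction blocked, and no reference level without GLP-2 is named for the table.
- *A weak blocker may not pass.* A reader might infer that it would pass easily. That holds only if the rise is large relative to the SD. At a rise of 1 SD, about 72% observed blockade is needed, and whether a physiological GLP-2 dose raises flow at all is one of the study's questions.
- *The same-day rise is not cleanly available.* A reader might take the scans from -32 minutes as giving it directly. The documents do not state the injection time or how many scans precede it. A rise over pre-infusion flow would also include any effect of the infusion and drift. This stands, and it determines the reference used in the fix.

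**Conclusion.** The point holds as a gap between aim and analysis. The primary test remains valid for showing a reduction. What lacks support is any statement about degree of blockade, and hence the choice of dose on that basis. The gap follows from the plan's text and needs no assumed figure.

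Its practical size does depend on assumptions. Over rises of 1 to 5 SDs, the observed blockade that reaches significance runs from 72% down to 14%, and a true 25% blocker is positive in 11% to 94% of trials. These figures rest on n = 10 with no dropout, two-sided 5%, and a paired t test as stand-in for the mixed model. The documents do not show where in that range the trial lies, so they do not support saying that a weak blocker will probably be declared effective. The remedy is cheap and worth making before the data are analysed, because a blockade measure chosen afterwards could be chosen to favour the claim.

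**What to change.** Keep the primary contrast, and state in full which two interventions it compares. For each antagonist dose, add to the analysis section and the planned table:

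(a) the paired difference in GLP-2-induced flow rise versus placebo infusion + GLP-2, with 95% CI;

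(b) the residual rise under the antagonist, with 95% CI;

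(c) percent blockade = 1 - (mean rise under antagonist + GLP-2)/(mean rise under placebo infusion + GLP-2), as a ratio of means with a Fieller or participant-level bootstrap 95% CI.

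Measure the rise from the last scan during the infusion before the GLP-2 injection, or from a no-GLP-2 condition if the design has one. Use pre-infusion flow only if no such scan exists, and then say that any infusion effect and drift are included.

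State that a significant primary contrast supports *reduces*, and that *blocks* or *maximal blocking* rests on (b) and (c).

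Cost: a few sentences in the plan and a little analysis, with no new scans or participants. The downside is precision. If the GLP-2 rise is small relative to the SD, (c) will be wide or unbounded, and (a) and (b) should then be relied on. The headline claim may also become less favourable.
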